### 9.2 Data Collection

Data for this specialized analysis will come from these sources:

1. Participant report of healthcare utilization (e.g. emergency department, urgent care, office) for all participants, these will focus on high-cost items and/or items that are expected to be sensitive to the intervention
2. Medicare claims data for Medicare enrollees
3. Medicaid claims data for Medicaid enrollees

*Participant reported visits:* Participant reported assessment for health care utilization is previously described in section 7.3.

*Medicare claims data:* For Medicare enrollees in fee-for-service (FFS) plans or Medicare Advantage, clinical groups will ascertain Medicare claims data (Part A-D) directly from the Centers for Medicare and Medicaid Services (CMS).

*Medicaid claims data:* For Medicaid enrollees, clinical groups will ascertain claims data from their states' Medicaid agencies directly.

To ensure full adjudication, requests to Medicare/Medicaid for claims data will be timed to occur between 6-12 months after the end of the 6-months follow-up of the last enrolled patient. Claims data will also be requested for one year before trial enrollment up to 6 months thereafter.

The procedure for obtaining claims data will require a database linkage step – mapping the participant study ID to the Medicare/Medicaid identifiers. The data linkage will rely on social security number (SSN) or Medicare ID and date of birth (DoB), which can be collected in two possible ways:

1. Both SSN and/or Medicare ID and DoB are collected as part of the trial by the recruiting site
2. One or both variables are extracted from the medical record of the participating health center by a healthcare data security officer or the local equivalent, on behalf of the study team

For **2020-2024 Medicare data**, we will have three groups:(1) Clinical Trial Participants: To achieve our goals to understand the effects of a genotype-guided approach, we will have all Medicare beneficiaries who participated in the ADOPT PGx clinical trial and enrolled in the trial. (2) Controls- a standardized national cohort based on the 5% sample of beneficiaries who did not participate the clinical trial but had similar characteristics with beneficiaries who participate the clinical trial (received opioids or antidepressants). We will further require beneficiaries to have at least 2 months of Part D and at least 2 months of FFS in the year that they received the opioid or antidepressant. (3) Controls – a cohort of beneficiaries from Florida, New York, North Carolina, Tennessee, South Dakota, and Indiana (the states in which the clinical sites are located), pulled from the 100% sample, in which the beneficiaries did not participate the clinical trial but have similar characteristics with beneficiaries who participate the clinical trial received opioids or antidepressants). We will further require beneficiaries to have at least 2 months of Part D and at least 2 months of FFS in the year that they received the opioid or antidepressant. The clinical trial participants will be used to evaluate the effects of immediate vs delayed pharmacogenetic testing and genotype-guided pain or depression therapy on health care utilization, healthcare costs, and cost-effectiveness. We will further compare the Medicare beneficiaries among the trial enrollees to large random sample of beneficiaries who take pain medications to compare demographics and clinical characteristics to explore representativeness of the trial sample, making inferences about generalizability of the results.

For **2020-2024 Medicaid data**, we will have two groups: (1) Clinical Trial Participants: we will have all Medicaid beneficiaries who participated in the ADOPT PGx clinical trial and enrolled in the trial. (2) Controls- a cohort of beneficiaries from Florida, New York, North Carolina, Tennessee, South Dakota, and Indiana (the states in which the clinical sites are located), in which the beneficiaries did not participate the clinical trial but have similar characteristics with beneficiaries who participate the clinical trial received opioids or antidepressants). We will further require beneficiaries to have at least 2 months of FFS in the year that they received the opioid or antidepressant.

For the Controls for Medicare and Medicaid beneficiaries, waiver of consent forms and HIPPA waiver of authorization will be obtained as the analyses of health care utilization and costs are retrospective in nature. It will be impracticable to obtain authorization from this population sample as patient contact information is unavailable.

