**Figure 1. ADOPT PGx Trial Design**

Intervention participants are denoted by blue boxes and blue lines, control participants are denoted by orange boxes and orange lines. Return of results are denoted with black outlines, endpoint comparison groups (actionable phenotypes in the control and intervention arms) are denoted with red outlines, and \* denote timing of the primary endpoint collection. Time 0 denotes the time from which the follow-up assessment timing begins.

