### **6.3 Participant Discontinuation/Withdrawal from the Study**

Participants may stop participating and withdraw from the study at any time. All information and data collected up until that point will be used in the study.

If a participant wishes to withdraw consent, they should contact study staff. A participant may also revoke HIPAA authorization and must provide the revocation in writing. Study staff may attempt to obtain a reason for withdrawal from the participant and record it in the study database.

In the acute pain trial, the principal investigators or clinical site investigators may withdraw a participant from the study for any of these reasons:

- Participant does not have the surgery within 12 months of study enrollment
- Participant has the surgery at a healthcare system that is different from where the participant enrolled
- Participant's surgery is scheduled for a date after the close of the enrollment period for that clinical site
- Participant is unable to have the surgery for other medical reasons

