### 7.3 Follow-up Participant Assessments

The event that starts the post-intervention data collection timing are as follows.

Acute Pain:

- Date of surgery (intervention and control arms)

Chronic Pain and Depression:

- Intervention arm: When the pharmacogenetics results are returned to the provider and deposited in the EMR
- Control arm: At date of DNA sample collection plus one week, where one week reflects the average time from sample collection to returning the results to the EHR
- Note: There will be variability in time the results are returned to provider and when genotype-guided therapy is delivered to the participant, time from results being available to the next provider-participant interaction (e.g. email, clinic visit, new prescription order, phone visit, etc.) will be recorded by study personnel.

Post intervention assessment collection may be done by the University of Florida College of PharmacyCall Center. The center agents will be trained survey collectors\*, using an IRB approved telephone script. The collected survey responses will be entered into the study database. If preferred, the participant will have the option to complete the study follow-up survey by a URL link sent by text (to mobile phone) or email and captured in REDCap database

In the event that the call center is unable to reach a participant, local study coordinators may contact participants to facilitate completion of the follow-up surveys.

Data will be collected in the following timeframes\*:

- Acute pain: 10 days, 1 month, 3 months, and 6 months post-surgery
- Chronic pain and depression: 1-month, 3 months, and 6 months post return of results for the intervention arm, and post baseline assessments for the control arm.

\*See *MOP for call center agents and survey collection interval windows*

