## 7.9 Data Collection from CMS and State Medicaid Agencies

Medicare and Medicaid claims data from CMS and state Medicaid agencies will be used to assess health care utilization, costs, and medications among participants covered by either Medicare or Medicaid. Claims made in the period of 12 months prior to surgery (acute pain) or return of results (chronic pain, depression) through 6 months following those events will be collected. See Section 9 and the MOP for additional details. Schedule of Activities and Timeframe for Collection of Endpoints

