**Table 8. Data collection schedule**

### Data collection schedule, method of data collection, and timing

Outcome	Data source/instrument	Baseline	10 d ± 3 d	1 mo. ± 7 d	3 mo. ± 14 d	6 mo. ± 14 d
Pain Assessments						
Pain intensity	PROMIS Pain intensity scales	AP, CP	AP	AP, CP	AP, CP*	AP, CP
Pain intensity	PROMIS Numeric Rating Scale - Pain Intensity (NPRS)	AP	AP*	AP	AP	AP
Daily opioid dose & type of opioid use	Average daily mg morphine equivalents (MED) since discharge use of opioids: tramadol/ codeine vs others		AP*	AP		
Opioid use disorder	PROMIS - Prescription pain medication misuse subscale	AP, CP			AP, CP	AP, CP
Mobility	PROMIS mobility	AP	AP	AP	AP	AP
Depression Assessments						
Depressive state	PROMIS Emotional Distress - Depression 8b survey	CP, D		CP, D	CP, D*	CP, D
Depressive state	Patient Health Questionnaire-8 depression scale	D			D	D
Participant Medications						
Assessment of prescriptions	Custom survey/EHR	AP, CP, D	AP		CP, D	
Assessment of filled prescriptions	Medicaid and Medicare billing records for 12 months prior to time 0 through 6 months after time 0		AP, CP, D			

Adherence	Voils Medication Adherence		D		D	D	D
SSRI AE Survey	Custom survey		D		D	D	D
Opioid side effect survey	Adapted medication side effect survey (SPACE)		AP, CP	AP	AP, CP	AP, CP	AP, CP
Opioid persistence	Custom survey						AP
Participant Actions							
Interaction with provider	Participant visits				CP, D		
Interaction with test result	Custom survey						AP, CP, D
Quality of life and well being							
Past Medical History	Participant visits/custom survey		AP, CP, D				
Well-being	PROMIS43/PROMIS Peds37		AP, CP, D		AP, CP, D	AP, CP, D	AP, CP, D
Healthcare Utilization and Costs							
Medicare/Medicaid billing records	Medicaid and Medicare billing records for 12 months prior to time 0 through 6 months after time 0				AP, CP, D		
LoS	LoS for index admission			AP			
ED/urgent care & inpatient visits	Participant reported visits				AP, CP, D	AP, CP, D	AP, CP, D
Outpatient visits	Participant reported primary care & pain clinic visits				AP, CP, D	AP, CP, D	AP, CP, D
Outpatient visits	Long-term care or in-patient rehab days, home healthcare days				AP	AP	AP
Productively Loss	Survey of lost work time and income				AP, CP, D	AP, CP, D	AP, CP, D

Abbreviations: CP – chronic pain, AP – acute post-surgical pain, D-depression, ED – emergency department, EHR – electronic health record; LoS – length of stay; PT – physical therapy

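### Section 9.2 dates the claims request from enrolment, not time 0, so a request cut to that rule would lose post-surgery months in acute pain; the window needs one definition

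*Combined protocol and SAP*

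**What the plan says.** The combined protocol and SAP describes the claims window in four places.

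- **Section 9.2** anchors it to enrolment: "Claims data will also be requested for one year before trial enrollment up to 6 months thereafter".
- **Section 7.9** anchors it to clinical events: "12 months prior to surgery (acute pain) or return of results (chronic pain, depression) through 6 months following those events".
- **Table 8**, which stands in 7.9, anchors it to time 0: "Medicaid and Medicare billing records for 12 months prior to time 0 through 6 months after time 0".
- **Section 10.6**, Cost Effectiveness, compares expenditures from an *index visit* to the 6-month follow-up. The term is not defined.

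The note to Figure 1 fixes the meaning of time 0: "Time 0 denotes the time from which the follow-up assessment timing begins". Section 7.3 then gives that start by trial and arm:

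- acute pain, both arms: date of surgery;
- chronic pain and depression, intervention arm: "Intervention arm: When the pharmacogenetics results are returned to the provider and deposited in the EMR";
- chronic pain and depression, control arm: DNA sample date plus one week, the week standing for the average time to return a result.

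Three other places bear on the point. Section 6.3 lists, among the reasons for which an acute pain participant may be withdrawn, "Participant does not have the surgery within 12 months of study enrollment". Section 7.5 has control samples processed only after the 6-month assessment. Section 9.1 says that all economic metrics cover a 6-month follow-up period, assumed to be free of cross-over effects from delayed testing in controls.

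**The concern.** Enrolment and time 0 are different dates. In acute pain the gap is the wait for surgery, which 6.3 allows to be long. An extract that stops 6 months after enrolment stops before the 6-month post-surgery period is complete for everyone who waits, and for a long wait it may contain none of it.

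Healthcare utilisation is an objective for all three trials in the synopsis, and 9.1 says that the economic results should inform reimbursement decisions. The claims also feed the cost imputation in 9.2, where claims and self-reported encounters from the same participants yield extrapolation factors for everyone else. Self-report in acute pain is timed from surgery. Claims cut by enrolment would be matched to it over a different period.

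A lesser question arises in 7.9. Controls in chronic pain and depression get their results only after 6 months, so return of results does not by itself name a usable start date for them.

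**Working it through.** There is no derived figure to reproduce. The plan's target is the 6-month follow-up period in 9.1, and the check is arithmetic on dates.

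**1. Section 9.2 in acute pain.** Let *d* be the months from enrolment to surgery. The 9.2 window ends at enrolment + 6. The period wanted runs from surgery to surgery + 6, that is from enrolment + *d* to enrolment + *d* + 6. The post-surgery months held are therefore max(0, 6 − *d*).

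| Wait *d* (months) | Post-surgery months held | Share of 6 |
|---|---|---|
| 0 | 6 | 100% |
| 1 | 5 | 83% |
| 2 | 4 | 67% |
| 3 | 3 | 50% |
| 4 | 2 | 33% |
| 6 to 12 | 0 | 0% |

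The pre-surgery year is not at risk: the window holds 12 + min(*d*, 6) months before surgery.

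The waits are assumptions. The documents give the 12-month point in 6.3 but no distribution. Acute pain is 2,020 of 4,522 planned participants in Table 9 (45%), or 1,730 of 1,730 + 985 + 1,540 = 4,255 in the synopsis (41%). These are the sizes of the trial in which the loss can occur, not counts of participants affected. Only those with claims data, put at 60% or more of the study population in 9.1, are affected directly.

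**2. Section 9.2 in chronic pain and depression.** The same formula applies, with *d* the lag from enrolment to time 0. The lag is not stated. With assumed lags of 1, 2 and 4 weeks (one week = 7/30.44 month), the months held are 6 − 0.23 = 5.77, 6 − 0.46 = 5.54 and 6 − 0.92 = 5.08 of 6.

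**3. Section 7.9, chronic pain and depression controls, literal reading.** Section 7.5 puts their results at about time 0 + 6 months. The window would then run from 6 − 12 = −6 to 6 + 6 = +12 months relative to time 0. The months labelled as follow-up would be 6 to 12, after delayed testing, and 6 of the 12 baseline months would be follow-up time. Months 0 to 6 would still be inside the extract, but under the wrong label.

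**4. The Table 8 rule.** With time 0 taken from 7.3, every participant in every trial and arm has 12 months before and 6 months after. For controls the window closes at about the time their delayed results are produced, which fits the assumption in 9.1.

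**The case against.** The best defence of 9.2 is that its sentence describes a data request and not the analysis window. The sentence says *also*, which can be read as adding to something wider. The sentence before it places the requests after the last participant's 6-month follow-up has ended, and 9.2 goes on to describe 2020–2024 Medicare and Medicaid data. Section 7.9 anchors acute pain correctly to surgery, 9.1 fixes a 6-month period, and details are left to the MOP and a separate SAP. Participant-reported utilisation is a parallel source.

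Much of this stands. The extract may well be wider than 9.2 says, and truncation follows only if the request is cut to that rule. But neither the word *also* nor a span of calendar years sets a window per participant, and 9.2 is the passage that states the request. It conflicts with 7.9 and Table 8, and nothing says which prevails.

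The 12 months in 6.3 is a point at which withdrawal may be considered, not an expected wait. The synopsis limits participation to one year from consent, which with 6 months of follow-up would imply waits of up to about 6 months. Even that shorter limit spans the whole range from no loss to complete loss.

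On 7.9, a reader might infer that control claims are to be taken from the wrong period. The documents do not support that. They use return of results as shorthand for the start of follow-up in both arms, including for the primary endpoints in 3.1 and the surveys in 7.3. The literal reading would move the controls' 3-month primary endpoint to about month 9. Section 7.3 supplies a stand-in date for controls, and Table 8 gives the time 0 rule within 7.9. What remains is an ambiguity.

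**Conclusion.** The point holds for 9.2. As written, its window conflicts with 7.9 and Table 8, and a request cut to it would hold max(0, 6 − wait) of the 6 post-surgery months in acute pain, from all 6 down to none. In chronic pain and depression the shift is probably small, provided that time 0 follows enrolment within a few weeks. The wording of 7.9 for controls is a separate ambiguity, and *index visit* in 10.6 needs a definition.

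The consequence is lost cost data in exploratory utilisation and cost-effectiveness analyses. No primary or listed secondary endpoint is touched. Waits for surgery should be similar in the two randomised arms, so the harm is probably lost information and understated follow-up costs more than bias between arms.

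Three stronger readings should be resisted:

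- That many participants have wrong follow-up periods: no distribution of waits is given.
- That control claims would contain post-testing months that intervention claims lack: in chronic pain and depression the intervention arm's results are returned at time 0, so all of its follow-up is post-testing.
- That time 0 should be the same event in both arms: 7.3 deliberately defines it by arm in chronic pain and depression.

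**What to change.** State one window in 9.2, 7.9 and the cost comparison in 10.6: 12 months before to 6 months after time 0, with time 0 as 7.3 defines it. That is surgery in acute pain, return of results in the chronic pain and depression intervention arms, and DNA sample date plus one week in their control arms. Replace *index visit* in 10.6 with this term. Section 7.3 also describes control follow-up as running from the baseline assessments; bring that wording into line with the sample-date rule.

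Make the claims request wide enough to reach 6 months after surgery for the longest wait. If waits reach the 12 months in 6.3, that means 12 + 6 = 18 months after enrolment.

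The cost is wording and a longer date range in the request. The requests are due 6 to 12 months after the last participant's follow-up ends. Correcting the text before they go out avoids a second request for the missing months.

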#### Costs imputation

The Medicare/Medicaid (M/M) claims will be used to impute healthcare utilization and costs for participants who are enrolled in other plans or not insured as follows. First, the subset of the study participants with both the participant reported set of medical encounters and M/M claims data will be identified. In this subgroup, claims data and self-report data will be used to derive extrapolation factors for total healthcare utilization and cost across all study participants. Additionally, for participants in other plans or uninsured, we will use M/M data to assign average cost to each of the self-reported items.

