## 7.8 Data Collection from the Electronic Health Record

Data collected from the local EHR will include prescription information and encounters including clinic visits, hospitalizations, and emergency department visits and associated diagnoses for the study interval time-zero through six-month follow up. Sites will extract data using prespecified programmatic algorithms, site-developed algorithms, and/or manual chart abstractions. EHR query results will be sent to the IGNITE PTN CC via secure data transfer and formatted for consistency across sites. Details for the EHR elements and transfer process will be provided in the MOP.

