#### Cost Effectiveness

*Healthcare costs:* In the Medicare fee-for-service or Medicaid enrollees, log-transformed overall expenditures (between index visit and 6 months follow-up) will be compared using a 2-sample t-test between the study arms (after ensuring that the variances in the log-scale are equal). Alternatively, cost comparisons will be made using appropriate regression models such as generalized linear models. For all participants, regardless of insurance type, we will estimate and aggregate participant-reported healthcare utilization during follow-up and assign cost for each item based on unit weighted mean cost estimates from the Medicare/ Medicaid data.

Within the Medicare/Medicaid population, we will compare estimated cost differences between genotype-guided and usual care based on billing records versus participant report to further validate the cost comparisons for the entire population. Cost for the index hospitalization for surgery participants will not be included in the cost estimate, but we will compare length of stay between groups as reference for hospitals regarding potential cost savings in capitation-based reimbursement schemes. All costs will be converted to 2021 \$US using the chain-weighted Consumer Price Index (CPI).

Finally, we will compare the Medicare/Medicaid beneficiaries among our trial enrollees to a larger random sample of beneficiaries in the participating states and compare demographic and key clinical characteristics to explore representativeness of our study sample, evaluate the impact of attrition and loss to follow-up and make inferences about the generalizability of our results.

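### The all-participant cost estimate prices reported encounters but no drugs, so an arm difference in drug cost cannot appear in it

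*Combined protocol and SAP*

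**What the plan says.** Section 9.1 takes the payer's perspective and aims to inform reimbursement of genotyping. Section 9.2 lists three sources for the economic data: participant-reported utilization, Medicare claims (Parts A to D) and Medicaid claims. Of the participant report it says "these will focus on high-cost items and/or items that are expected to be sensitive to the intervention".

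Under Costs imputation, section 9.2 gives two routes for people without claims:
- **Factor route.** It starts from the subgroup with "both the participant reported set of medical encounters and M/M claims data". There, "claims data and self-report data will be used to derive extrapolation factors for total healthcare utilization and cost across all study participants".
- **Item route.** It adds that "for participants in other plans or uninsured, we will use M/M data to assign average cost to each of the self-reported items".

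Section 10.6 (Cost Effectiveness) applies item costing to all participants, whatever their cover: "we will estimate and aggregate participant-reported healthcare utilization during follow-up and assign cost for each item based on unit weighted mean cost estimates", with the unit costs taken from Medicare/Medicaid data. It also compares claims-based expenditure between arms in Medicare fee-for-service or Medicaid enrollees. Within the Medicare/Medicaid population it sets the arm difference from billing beside the arm difference from self-report.

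Drug data exist for everyone. Section 7.8 states: "Data collected from the local EHR will include prescription information and encounters including clinic visits, hospitalizations, and emergency department visits", from time zero to six months. Section 7.3 adds a medication survey and, in Acute Pain, an opioid consumption questionnaire. None of these is among the three economic sources in 9.2, and none is given a price.

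**The concern.** Section 7.1 describes an intervention that acts on prescribing: which opioid is avoided or replaced, and which antidepressant is chosen or at what starting dose. Drug spending is therefore the cost it touches most directly. Any effect on visits comes later, through better or worse symptom control. A cost estimate built only from encounters leaves out the first and can see only the second.

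At stake are the average cost per arm for the whole trial population and, if that cost series is the one used, the incremental cost-effectiveness ratio. Section 10.6 does not say which cost series feeds the ratio. A payer given an all-participant figure without drugs would not have the net cost of a drug-selection strategy.

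**Working it through.** **1. Which sources carry drug information, and which are priced**

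| Source | Who and when | Drug content | Priced? |
|---|---|---|---|
| Utilization survey (7.3, Table 8) | All, during follow-up | None named; visits, plus long-term-care, rehab and home-care days in Acute Pain | Yes (9.2, 10.6) |
| Medicare/Medicaid claims (7.9, 9.2) | Covered participants | Yes | Yes |
| EHR (7.8) | All, time zero to 6 months | Prescription information | No |
| Medication survey (7.3) | All, baseline and 10 days or 3 months | Medications | No |
| Opioid consumption questionnaire (7.3) | Acute Pain, 10 days and 1 month | Opioid type, pill counts, refills | No |

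The only priced source that covers everyone has no named drug item.

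**2. How many participants may lack claims**

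Section 9.1 expects claims for at least 60%. Adding its Medicare and Medicaid shares:
- knee arthroplasty: 53 + 4 = 57%
- hip arthroplasty: 59 + 4 = 63%
- chronic pain: 40 + 20 = 60%
- mean: (57 + 63 + 60)/3 = 60%

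So 60% reproduces as a central value. It is not a floor, because knee is at 57% before any enrollment gaps. The shares without claims are 43%, 37% and 40%. No figure is given for depression. Assuming 37% to 43% throughout:
- Table 9 total: 0.37 × 4,522 = 1,673 to 0.43 × 4,522 = 1,944 participants.
- Synopsis total (1,730 + 985 + 1,540 = 4,255): 1,574 to 1,830 participants.

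These are the people with no drug cost from any priced source. The item-costed estimate in 10.6 omits drugs for covered participants as well.

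**3. What each method can recover**

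Let V be mean encounter cost and D mean drug cost, with subscript 1 for intervention and 0 for control, and equal arms.
- True difference: (V1 − V0) + (D1 − D0)
- Item costing: V1 − V0. D1 − D0 is absent whatever its value.
- One pooled multiplier: f = [(V0 + D0) + (V1 + D1)]/(V0 + V1), giving f × (V1 − V0). If visits are equal this is zero.
- Arm-specific multipliers: fa = (Va + Da)/Va, giving f1V1 − f0V0, which equals the true difference if drug-to-visit ratios are the same with and without claims.

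**4. Illustration with assumed costs** (USD per person; the documents give none)

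| | V0, V1 | D0, D1 | True | Item costing | Pooled factor | Arm-specific |
|---|---|---|---|---|---|---|
| (a) | 3,000, 3,000 | 300, 400 | +100 | 0 | 6,700/6,000 = 1.117; × 0 = 0 | +100 |
| (b) | 3,000, 2,800 | 300, 500 | 0 | −200 | 6,600/5,800 = 1.138; × −200 = −228 | 0 |

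The table shows how the methods behave. It does not estimate what will happen in this trial.

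**The case against.** The case for leaving the plan alone has several parts.

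- **A drug-inclusive comparison already exists.** Section 10.6 first compares claims-based expenditure between arms in Medicare fee-for-service or Medicaid enrollees. This stands. The gap lies in the extension to all participants.
- **A check is already planned.** Comparing billed with reported cost differences could reveal missing drug cost. This also stands, but no correction follows from it.
- **The factor may be meant to cover drugs.** Section 9.2 offers it in addition to item costing, for total cost. A reader might infer that drug cost is forced to move with visits. The documents do not support that: the factor is not said to be pooled, common to both arms or multiplicative, and an arm-specific form could recover the mean difference.
- **The survey lists are examples.** Section 9.1 mentions resource questionnaires whose content is not shown, and Acute Pain has an opioid questionnaire. But no drug item appears in the utilization rows of Table 8. The opioid questionnaire covers one trial and one drug class up to 1 month, and is not linked to cost.
- **A large distortion is not shown.** A reader might infer a reversed sign from examples like (b). That rests entirely on assumed dollars. If drug changes were confined to actionable participants, even a USD 100 arm-wide difference would need 100/0.18 = USD 556 each in Acute Pain, 100/0.30 = USD 333 in Chronic Pain and 100/(0.40 × 0.67) = USD 373 in Depression. Pain recommendations also reach normal and ultra-rapid metabolizers, so the dilution there is only partial.
- **Details are deferred.** Further statistical detail is left to the SAP and data-collection detail to the manual of operations, and this analysis is exploratory. That lowers the priority. It does not change the method the protocol states.

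**Conclusion.** The point holds as a gap in an exploratory analysis. As written, the item-costed all-participant estimate in 10.6, and the item costing in 9.2 for those without claims, cannot show an arm difference in drug cost. Whether the extrapolation factor repairs this is undetermined, because its form is not stated; a single pooled multiplier on visits would not.

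The size and direction of the error are unknown. It would also be wrong to infer that the share with claims is the share of a drug-cost difference that is recovered. That would require claims totals to be combined with a common factor elsewhere, whereas 10.6 costs everyone from reported utilization.

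The conclusion assumes that the utilization survey contains what 7.3, Table 8 and 9.2 describe. If the resource questionnaires do record priced drug quantities, the plan need only say so. Primary and secondary efficacy analyses are unaffected.

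**What to change.** In 9.2 (Costs imputation) and 10.6 (Cost Effectiveness):

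1. Add drug cost as a separate component for every participant. Price the EHR prescriptions collected under 7.8 at Medicare/Medicaid mean unit drug prices, identically in both arms. Supplement them with the medication survey and, in Acute Pain, the opioid consumption questionnaire.
2. Limit any extrapolation factor to categories not captured directly. State its form, including whether it is estimated by trial and by arm.
3. Check the drug component against claims in covered participants, as an extension of the billing-versus-report comparison already planned.
4. State which cost series enters the incremental cost-effectiveness ratio.

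The cost is SAP wording and programming. There are limitations to disclose: EHR orders are not fills, prescribers outside the health system may be missed, and quantity or days' supply may have to be assumed, since 7.8 promises prescription information without naming those fields.
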